# 9.3 Inclusion criteria for subject selection

- Patient requires primary hip arthroplasty due to degenerative joint disease (primary osteoarthritis, posttraumatic osteoarthritis, avascular necrosis, developmental hip dysplasia)
- Patients femoral bone stock is adequate for hip resurfacing on plain radiographs
- Patient is between 18 and 70 years old
- Patient willing to comply with study requirements
- Patient plans to be available through ten (10) years postoperative follow-up
- Patient is able to understand the native language of the country where their procedure is taking place

# 9.4 Exclusion criteria for subject selection

- Patient has a BMI greater than 40
- Patient suffers from an active inflammatory joint disorder
- Patient has an active infection or sepsis (treated or untreated)
- Patient has insufficient bone stock at the hip (>1/3 necrosis of the femoral head)
- Patient has severe osteopenia or osteoporosis, defined using DXA by T-score of
   <-2.5 (if T-score does not meet the criteria, please confirm with coordinating site (ICL) for participant eligibility)

- Patient has large and multiple cysts in the femoral head (patients with cysts to be reviewed by coordinating site (ICL) for participant eligibility)
- At the time of enrolment, patient has one or more of the following arthroplasties that have been implanted less than 6 months before the current hip arthroplasty:
  - $\circ$  Contralateral primary total hip arthroplasty or hip resurfacing arthroplasty
  - $\circ$  Ipsilateral or contralateral primary total knee or unicondylar knee arthroplasty
- Patient takes medications which potentially affect the bone such as corticosteroids and antimitotic medications.
- Patient has a condition that may interfere with the hip arthroplasty survival or outcome (i.e., Paget's or Charcot's disease, vascular insufficiency, muscular atrophy, uncontrolled diabetes, moderate to severe renal insufficiency or neuromuscular disease)
- Patient has a known alcohol or drug abuse
- Patient has an immunosuppressive disorder
- Patient has a malignant tumour, metastatic, or neoplastic disease
- Patient has severe comorbidities or a limited life expectancy
- Patient lacks capacity to consent
- Patient has an emotional or neurological condition that would pre-empt his/her ability or willingness to participate in the study
- Patient is not willing or able to sign an informed consent form
- Patient pregnant or breast feeding
- Patient is not able or willing to come to follow-up visits
- Any other clinical reason, which the investigator considers would make the patient unsuitable for the trial

– Implant size unavailable

In addition, the following exclusion criteria are applied to the patients in the safety study in whom metal ion measurements will be performed, since those conditions may be associated with elevated metal ion levels and could complicate the interpretation of the metal ion results [41]:

- Patients who already received another joint replacement, hip, knee, shoulder, ankle
- Workers in the paint, diamond, leather or other industries producing Co or Cr dust
- Patients taking medication, vitamins or food supplements containing Co or Cr and not able or willing to discontinue those.

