#### 9.2.2 Staggered Bilateral HRA

Patients who are enrolled into the study as part of Cohort 1A, Cohort 1B or 2 can undergo a HRA with a H1 implant on the contralateral side if they meet the inclusion/exclusion criteria, and pass the screening assessments. All staggered bilateral patients recruitment must be re-consented for the additional assessments before taking part in the study for their contralateral hip. At point of re-consent these patients will be registered again with the coordinating site for a unique identification number for their contralateral second hip.

Patients recruited in cohort 1A who opt to undergo HRA for the contralateral hip will follow the assessments as detailed in Table 6. Those patients in cohort 2 who opt to

undergo HRA for the contralateral hip will follow assessments as detailed in Table 7. Patients recruited in cohort 1B will follow the assessments as detailed in Table 8. These patients will undergo additional AP and Lateral radiographs and will be required to complete the following questionnaires for the contralateral second hip: Oxford Hip Score, EQ5D-5L, Harris Hip Score and Imperial Score (online only).

Bilateral and staggered bilateral patients can be recruited from all sites participating in the trial, however the total number of bilateral implants cannot exceed 20% of the total study sample size (250). Therefore only 25 patients (50 hips) can be recruited as a bilateral or staggered bilateral patient, once this number has been reached, recruitment for the contralateral hip will cease and recruitment will continue for uni-lateral hips only. Bilateral patients and those recruited for the contralateral hip as staggered bilateral patients will be registered as a separate patient for each hip with a unique trial identification number for both hips. Case Report Forms will be completed for each hip.

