#### 10.1.2 Secondary Objective - Safety Study

Regarding the safety analysis, the sample size is calculated based on the superiority of the ceramic-on-ceramic bearing couple compared to MoM hip resurfacings. Several studies [22] have demonstrated that ceramic bearings are not associated with metal ion release (levels below detection limits of most labs i.e. < 0.5 µg/L). Previous research [3] investigated metal ion measurements from well-functioning MoM unilateral hip resurfacings (n = 251) and found mean cobalt (Co) levels of 1.8 µg/L (median 1.5 µg/L – SD 1.2) and mean chromium levels of 2.0 µg/L (median 1.6 µg/L – SD 1.2). The Co and Cr levels of the ceramic-on-ceramic hips are expected to be < 0.5 µg/L. Thus 14 subjects in each group are required to achieve  $100(1 - \beta) \% = 80\%$  power to detect a difference in the mean Co levels at the Significance level of  $\alpha = 0.05$  (NCSS statistical software).

In order to account for patients lost to follow-up, unavailability or loss of blood samples or laboratory problems with measurements, 20 patients will be included in the metal ions investigation.

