# Table 5. Schedule of procedures: Cohort 2 simultaneous bilateral patients – All sites (except \* which are UK sites only and \*\* which are online only)

		_						Post-op				
	Date	Pre-op	Op day	2 days	6 weeks	6 months	1 year	2 years	3 years	5 years	7 years	10 years
	Deviation window	≤4 mos prior	0	±1 day	±2 weeks	±2 weeks	±2 weeks	±4 weeks	±4weeks	±3 months	±3 months	±3 months
	Informed consent	✓										
	Inclusions/exclusions	√ √										
	Patient registration	√√										
	DXA Scan	✓ ≤12 mos prior										
	Medical history	√ √										
	Operative data		$\checkmark\checkmark$									
	Treadmill gait*	√*					√*			√*		
ient	Harris Hip Score	√ √			√√	√ √	√ √	√√	√√	√√	√ √	√√
Assessment	Oxford Hip score	√ √			$\checkmark\checkmark$	√ √	$\checkmark\checkmark$	√ √	$\checkmark\checkmark$	√ √	$\checkmark\checkmark$	$\checkmark\checkmark$
Asse	Imperial Hip Score**	√√**			√√**	√	√√ **	√√**	√√**	√√ **	√√ **	√√**
	EQ-5D	√ √			~~	√ √	√√	~~	√ √	~~	√ √	√ √
	AP Radiographs	✓ ≤12 mos prior		✓	✓		~	~	~	~		✓
	Lateral Radiographs	

✓✓ ≤12

mos prior

		~~	~~		√ √	~~	√ √	~~		√ √
	Low dose CT scan*	<pre>✓*^ ≤12 mos prior</pre>										
	Conmed questions	√ √	√ √	~ ~	~~	√ √	√√	~~	√ √	~~	√√	√ √
	Record Adverse Event(s)	vv	~ ~	~~	√ √	√ √	√ √	√ √	√√	√ √	√√	√√

 $\sqrt{4}$  = Separate assessments to be taken for both hips

### Table 6. Schedule of procedures: Staggered bilateral patient recruited from Cohort 1A into Cohort 2

	t Study Hip hort 1A)	Pre-op	Op day	2D	6 wks	3 mos	6 mos					1 year			2 years		3 years		4 years	5 years		6 years	7 years		8,9 years	10 years	
	tralateral Second dy Hip (Cohort 2)							Pre-op	OP Day	2 D	6 wks		6 mos	1 year		2 years		3 years			5 years			7 years			10 years
	Re-consent for contralateral Hip				1	1		 																			
	Inclusion/exclusion							 																			
	Patient registration							 																			
	DXA Scan							√^ ≤12 mos prior																			
	Medical History							 																			
	Operative data								 																		
ţ	Treadmill gait							 				✓		 						✓	 						

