#### Table 8. Schedule of procedures: Staggered bilateral patients recruited from Cohort 1B into Cohort 2 or vice versa

Col	hort 1B Study Hip	Pre-op	Op day	2D	6 wks	3 mos	6 mos	9 mos					1 year		2 years		3 years			4 years	5 years		6 years	7 years		8,9 years	10 years	
Col	hort 2 Study Hip								Pre-op	Op day	2D	6 wks		6 mos		1 year		2 year	3 year			5 years			7 years			10 years
	Informed consent								~																			
	Inclusions/exclusions								~																			
	Patient registration								~																			
	DXA Scan								√^ ≤12 mos prior																			
	Medical History								 																			
	Operative data									 																		
L	Treadmill gait								 				✓			 					✓	 						
Assessment	Harris Hip Score	Ass	essm	nents	don	e as r	oer Ta	able	 			 	~	 	✓	 	✓	 	√		✓	 		~	 		✓	 
sess	Oxford Hip score				3				 			 	~	 	✓	 	✓	 	 	✓	✓	 	~	~	 	~	✓	 
As	Imperial Hip Score								 			 	~	 	✓	 	✓	 	 	✓	✓	 	~	~	 	~	~	 
	EQ-5D								√			 	~	 	✓	 	✓	 	 	✓	✓	 	~	~	 	~	✓	 
	AP & lateral Radiographs								√ ≤12 mos prior		~	 				 	✓	~	 		~	 					✓	~
	Low dose CT scan								⊻ ≤12 mos prior																			
	Ultra low dose CT												~		✓													
	Conmed questions								~	√	√	√	~	√	~	 	✓	 	√	✓	✓	√	~	✓	√	✓	✓	 
	Record Adverse Event(s)								 	 	~	 	~	 	~	 	✓	~	 	~	~	 	~	~	~	~	~	~

 $\checkmark$  = Cohort 1B Study Hip  $\checkmark$  = Cohort 2 Study Hip  $\checkmark$  = To be taken only if previously DXA scan not done

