## Table 9. Schedule of procedures: Staggered bilateral patient recruitment from Cohort 1A into Cohort 1B

	t Study Hip hort 1A)	Pre-op	Op day	2D	6 wks	3 mos	6 mos						1 year				2 years		3 years		4 years		5 years		6 years		7 years		8,9 years		10 years	
	tralateral Second dy Hip (Cohort 1B)							Pre-op	ОР Day	2 D	6 wks	3 mos		6 mos	9 mos	1 year		2 years		3 years		4 years		5 years		6 years		7 years		8,9 years		10 years
	Re-consent for contralateral Hip							 																								
	Inclusion/exclusion							~																								
	Patient registration							 																								
	DXA Scan							√^ ≤12 mos prior																								
	Medical History							√																								
	Operative data								$\checkmark$																							
t	Treadmill gait							√					~			 							✓	 								
sme	Harris Hip Score	Ass	essm			e as pe	er	√			 	 	~	 	 	 	✓	 	✓	 			✓	 			✓	 			✓	$\checkmark$
Assessment	Oxford Hip score			Tab	le 2			 			 	 	~	 	 	 	✓	 	✓	$\checkmark$												
◄	Imperial Hip Score							√			 	 	~	 	 	 	✓	 	~	 	✓	 	✓	 								
	EQ-5D							√			 	 	~	 	 	 	✓	 	✓	$\checkmark$												
	AP & Lateral Radiographs							√ ≤12 mos prior		 									~	~			~	 							~	~
	Ultra low dose CT									 	 	 	✓	 	<	 	✓	 														
	Metal lons bloods*							 				 	✓	 		 	✓	 														
	Conmed questions							 	 	 	 	 	~	 	 	 	✓	 	~	 	✓	 	~	 	✓	 	✓	 	~	 	✓	✓
	Record Adverse Event(s)							 	~	~	~	~	~	~	~	 	~	~	~	~	✓	 	~	 	✓	 	~	 	~	 	~	~

 $\checkmark$  = First Study Hip  $\checkmark$  = Contralateral Second Hip  $\checkmark$  = To be taken only if previously DXA scan not done \*Metal ions questionnaire and bloods only taken for first 14 patients

CIP Version: Version 8 02.10.2020 IRAS ID: 213102

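### Table 9 schedules metal-ion bloods for second hips that section 9.4 makes ineligible, and Table 8 omits 12- and 24-month samples that Table 3 and section 11.8 require

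*Protocol*

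**What the plan says.** Section 9.4 adds criteria for the patients whose metal ions are measured. The first excludes "Patients who already received another joint replacement, hip, knee, shoulder, ankle". The stated reason is that such conditions "may be associated with elevated metal ion levels and could complicate the interpretation of the metal ion" results.

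Section 9.2.2 allows patients in any cohort a staggered second H1: they "can undergo a HRA with a H1 implant on the contralateral side if they meet the inclusion/exclusion criteria" and pass screening. Each hip is then registered as a separate patient with its own trial number. This section sends Cohort 1A patients to Table 6, Cohort 2 patients to Table 7 and Cohort 1B patients to Table 8. It does not mention Table 9, and sections 11 and 11.3.4 cite only Tables 2 to 8.

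Table 9 covers a Cohort 1A patient whose second hip enters Cohort 1B. Its metal-ion row has ticks for the second hip, with the footnote "Metal ions questionnaire and bloods only taken for first 14 patients". Table 8 covers "Staggered bilateral patients recruited from Cohort 1B into Cohort 2 or vice versa" and has no metal-ion row. Table 3 and section 11.8 call for bloods pre-operatively and at 3, 6, 12 and 24 months; Table 3 limits this to the first 14 Cohort 1B patients.

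Section 10.1.2 takes its reference values from 251 unilateral MoM resurfacings, requires 14 subjects per group and plans 20.

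**The concern.** Eligibility and the sampling schedule are both fixed in the protocol, and here they disagree. A site that follows Table 9 measures metal ions in a person whom section 9.4 excludes from that measurement. Because hips are numbered as patients, the first-14 rule can count that second hip.

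The set is small and carries weight. Cohort 1B toxicology is part of Gateway Safety Analysis 2 at 6 months in Table 1, the Cohort 1B analysis after which section 8.3.2 allows Cohort 2 recruitment to resume. Sections 8.2.2 and 8.2.3 make the decision not to test all patients conditional on these cohorts showing no metal-ion release at 3, 6, 12 and 24 months. An ineligible record in the set, or two missing time points, weakens both uses.

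**Working it through.** **Step 1. Schedules against the eligibility rule**

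| Table | Pathway | Metal-ion bloods shown | Relation to 9.4, Table 3 and 11.8 |
|---|---|---|---|
| 9 | 1A hip, then 1B hip | Second hip: pre-op, 3 and 6 months, 1 and 2 years. First hip: 1 and 2 years | The second-hip samples contradict 9.4: the patient already has an H1 |
| 8, 1B hip first | 1B hip, then Cohort 2 hip | None; Table 3 applies only up to 9 months | The 12- and 24-month samples are lost for a first-14 patient |
| 8, Cohort 2 hip first | Cohort 2 hip, then 1B hip | None | Agrees with 9.4 |
| 6 | 1A hip, then Cohort 2 hip | First hip: 1 and 2 years | No breach of 9.4; samples are drawn after the second operation as the table is laid out |

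Table 9 has three consequences:
- An ineligible hip can take one of the 14 places.
- One person can appear as both a 1A and a 1B toxicology record.
- The second hip's pre-operative sample is drawn with an H1 in place.

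The second hip's 3- and 6-month samples are also on the schedule, so the 6-month gateway report can be reached, not only the later reports.

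**Step 2. Reproduce the stated sample size**

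Inputs from section 10.1.2: mean Co 1.8 µg/L and SD 1.2 in MoM hips, H1 level taken at 0.5 µg/L, alpha 0.05, power 80%. Sidedness is not stated; two-sided is assumed.

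n per group = 2(1.96 + 0.842)² × 1.2² / (1.8 − 0.5)² = 13.4, rounded up to 14.

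This matches. Power at 14 is 0.818 by the normal approximation. A t-test gives 14.4, hence 15, with power 0.788 at 14.

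**Step 3. Weight of one record and the reserve**

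One record is 1/14 = 7.1% of Cohort 1B and 1/20 = 5% of Cohort 1A. Cohort 1A has 20 − 14 = 6 in reserve over the stated requirement. Cohort 1B has 14 − 14 = 0.

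| Records left | Equal-arm power (normal approximation) |
|---|---|
| 14 | 0.818 |
| 13 | 0.789 |
| 12 | 0.756 |
| 10 | 0.678 |

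Against all 251 historical hips, t-test power is still 0.917 with 10 records. Leaving a few records out therefore costs little in the cobalt comparison.

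**Step 4. What two-hip samples would do to cobalt**

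Assumption, not in the protocol: 1.0 µg/L with two hips against 0.5 with one.

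| Sampled | Two-hip patients | Mean Co (µg/L) | Power |
|---|---|---|---|
| 14 | 1 | (13 × 0.5 + 1.0)/14 = 0.536 | 0.796 |
| 14 | 4 | (10 × 0.5 + 4.0)/14 = 0.643 | 0.723 |
| 20 | 1 | (19 × 0.5 + 1.0)/20 = 0.525 | 0.919 |
| 20 | 4 | (16 × 0.5 + 4.0)/20 = 0.600 | 0.885 |

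The shift runs against superiority. If two-hip levels also stay below 0.5 µg/L, the cobalt conclusion does not change.

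**The case against.** The strongest reply is that little harm can follow. Section 8.3.1 says the material contains no cobalt, and chromium is expected below detection. A second H1 can only add ions, so absence with two hips implies absence with one. This stands for the superiority claim. It does not settle which records belong in the set or whether they are independent.

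A second reply is that section 9.4 already governs, since 9.2.2 makes second hips meet the eligibility criteria. But every second-hip tick in Table 9's metal-ion row is for a patient with an H1, so the row and the rule cannot both be followed.

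A reader might infer more than the documents support:
- **That Table 6 breaches 9.4.** The criterion concerns replacements already received and works at entry. A Cohort 1A patient met it then, and continued sampling is ordinary follow-up.
- **That Table 8 mixes exposures.** It loses samples. It does not mix them.
- **That a given share of the 12- and 24-month values are two-hip values and biased.** The protocol gives only an overall cap of 25 bilateral patients, not the number in these subsets. Timing also limits the Table 6 route. Hips must be at least 6 months apart, and Cohort 2 was suspended on the Cohort 1A 6-month data and resumes only after Cohort 1B's 6-month analysis. A Cohort 1A patient joining Cohort 2 after resumption would probably be past the first hip's 12-month visit.
- **That titanium or change from baseline is distorted.** Titanium is expected during bone ongrowth, so a second cementless hip could add some, but the protocol gives no figure. Its stated comparison is of levels with historical MoM values, not of change from baseline.

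**Conclusion.** Two inconsistencies hold on the face of the protocol: Table 9 against section 9.4, and Table 8 against Table 3 and section 11.8 when the 1B hip came first. Table 6 raises a lesser matter: some first-hip samples at 1 and 2 years may follow a second H1 while the reference is unilateral, and the protocol text gives no rule for telling them apart.

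Each Table 9 second hip that is sampled is 7.1% of a 14-record set with no reserve. Each affected Table 8 patient loses two of the four post-operative samples. All of this depends on staggered bilateral patients actually occurring in these subsets, and the protocol does not say how many do. A changed cobalt result is not shown and is unlikely on the protocol's own expectations. The correction should still be made, because the 14-record set feeds the gateway report and the condition for not testing further patients.

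**What to change.** Reconcile sections 9.2.2, 9.4 and 11.8 with Tables 6, 8 and 9:

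1. **Table 9:** remove the second-hip metal-ion bloods. The remaining ticks are Cohort 1A first-hip samples, which section 8.2.2 requires in all Cohort 1A patients, so the first-14 footnote should go too. Refer to Table 9 in 9.2.2 and section 11.
2. **The 14:** define them as the first 14 Cohort 1B patients who meet the extra criteria in 9.4, so that a Cohort 1A patient's second hip does not count. Carry the same limit into 11.8, which now names Cohort 1B without it.
3. **Table 8:** add the 1- and 2-year metal-ion samples for first-14 patients whose 1B hip came first. Leave the row empty where the Cohort 2 hip came first.
4. **Samples after a second H1:** flag them on every pathway and report them separately from the comparison with unilateral MoM hips.

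The cost is a few table edits and one sentence on the toxicology set. A few late samples leave the main comparison, so it becomes slightly less precise.

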# 9.5 Subject withdrawal

All reasonable efforts should be made to retain the patients for the 10-year duration of the investigation. However, participation is voluntary and patients may withdraw at any point. A final evaluation including questionnaires will be completed for all patients who do withdraw, and the reason for the withdrawal will be documented on the enrolment and withdrawal form. After a patient withdraws from the study, he or she will be further followed outside the study preferably by the surgeon who performed the hip arthroplasty. Any patients withdrawn due to an adverse event will be followed-up by the Chief Investigator until the adverse event has been resolved or stabilised.

The investigator may also discontinue patients due to non-compliance with visits and assessments or if the patient is simply lost to follow-up.

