#### **Secondary Endpoints**

- Complication rate (adverse events and revisions)
- Toxicology (blood metal ion measurements)
- CT assessment (Implant migration)
- Patient Reported Outcome Measures (PROMs)
- Objective clinical and functional outcomes (Harris Hip Score, Gait Analysis)
- Radiological assessment (implant orientation, osseointegration)

The primary endpoint will be revision of the H1 prosthesis for any reason. However, since hip resurfacing components are considered to be easy to revise, the threshold for revision may be lower than for a total hip arthroplasty. Therefore, the secondary endpoints of the H1 ceramic-on-ceramic and comparison with Metal-on-metal hip resurfacing and with conventional Total Hip Arthroplasties is considered to be a very important discriminating factor as well. Secondary endpoints will investigate the short-(6 months, 1 year, 2 years, 3 years), mid- (5, 7 years) and long-term (10 years) safety and efficacy of the H1 hip resurfacing prosthesis for the whole patient cohort.

In the Cohort 1A and 1B, cementless acetabular and femoral component migration, and bone ongrowth will be assessed on low-dose CT scans. Absence of generation of metal wear debris potentially leading to local adverse tissue reactions and systemic toxicity will also be assessed by measuring metal ions (cobalt, chromium) in whole blood. Metal ion blood levels will be compared to historical metal ion measurements from MoM hip resurfacings and publications in the orthopaedic literature.

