# 10.2 Statistical Analysis

A non-inferiority test of the cumulative percent success (defined in section 2) in subjects implanted with the H1 hip resurfacing compared to a literature reference rate will be the primary test of efficacy in this study. The null hypothesis is H0:  $\pi_0 - \pi \ge 0.05$  and the alternative hypothesis is Ha:  $\pi_0 - \pi < 0.05$ .

Primary and secondary outcomes will be evaluated using listings and summary statistics. A confidence interval of 95% will be calculated for proportions and averages. Improvement in pain and function will be analysed using parametric (t-test) or non-parametric (Wilcoxon Rank tests) as appropriate. A Kaplan Meier survival estimate will be calculated in this study. For the survivorship analyses, revisions are defined as revision for any reason. Prognostic factors will be adjusted, if necessary, using parametric or non-parametric analyses (log Rank; Cox regression). All statistical analyses and calculation of confidence intervals will be performed using appropriate statistical software packages.

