#### 10.3 Missing data

In order to evaluate the potential impact of interim and final analyses, the reason of non-completed Patient Reported Outcome Measures Forms, or Radiographic Evaluation will be provided in the analysis reports. A complete accountability report, along with the explanation for lost-to-follow-up, death, revision, and withdrawn patients, is to be provided in the interim and final study analyses.

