#### 11.3.5 Follow-up Procedures – remote visits

All effort will be made to ensure patients attend their follow up visits. However if a patient is unable to attend for a particular reason, they will be followed up remotely (phone, skype and/or email) so that no data is missed. If the patient has an imaging scan locally and is able to get a copy of this data, a copy should be retained and used as part of this scheduled visit point. If no imaging scan has been taken, then this will be noted down as a missed data collection point.

The following data points will be collected

- All Adverse Events and Serious Adverse Events must be reported.
- Concomitant medication recorded.
- Modified Harris Hip Score will be collected in place of Harris Hip Score
- Patient Reported Outcome Measures (see Section 11.5)
  - UK Sites via JointPRO (OHS, EQ5D, IHS) or paper based questionnaires over skype/phone/email (OHS, EQ5D)
  - Non UK sites Paper based questionnaires over skype/phone/email (OHS, EQ5D)

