#### 11.9 Lost to Follow-up

Some actively enrolled subjects will not return for their follow-up visits due to a variety of reasons. The investigator/study site must use every reasonable measure to obtain follow-up clinical data: phone calls, regular mail and e-mail, certified letters to urge subjects to return for clinic follow-up or ascertain if a patient has moved, died, or otherwise become lost to follow-up. Reasons for loss to follow-up will be recorded if known.

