# 18 Suspension or Premature Termination of the Clinical Investigation

Analysis reports are scheduled as outlined in Table 1. If the analysis report is said to have a significant impact on patient safety, the study will be suspended or terminated accordingly. If the study is temporarily suspended, a full report will be sent to both the ethics committee and competent authority with corrective plans and actions to allow for continuation of the study. While the study is suspended, no new patients will be recruited, however patients registered thus far will continue to follow the schedule of visits as detailed in the table of schedule of procedures. If the study is terminated, patients will be contacted and the findings discussed at the earliest time possible. Patients will be invited back to clinic to discuss the issue with them.

Patients lost to follow up or who choose to withdraw will be followed up by healthcare professionals accordingly. The investigator will decide on the nature and frequency of the follow-up as long as the patient is happy with it. For example, the investigator may deem it acceptable to follow up via telephone call, where they may be asked about adverse events if the patient is happy for the follow up to continue this way. If the study is terminated early, these patients will be notified and asked to attend a clinic appointment for further discussion.

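### Section 9.5 lets investigators discontinue patients for missed visits without requiring revision status afterwards, so the primary endpoint may be censored avoidably and H1 survival could be overstated

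*Protocol*

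**What the plan says.** Section 8.1.3 of the protocol sets the endpoint: "The primary endpoint will be revision of the H1 prosthesis for any reason". Section 10.1.1 tests 10-year success against a fixed 93% reference with a 5-point margin and allows for 10% loss to follow-up by 10 years. Section 10.2 adds: "A Kaplan Meier survival estimate will be calculated in this study".

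Four sections deal with patients who stop attending:

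- **Section 9.5** opens by asking for reasonable efforts to retain patients for 10 years. Of a patient who withdraws it says "he or she will be further followed outside the study preferably by the surgeon who performed the hip arthroplasty". It ends with the permission at issue: "The investigator may also discontinue patients due to non-compliance with visits and assessments or if the patient is simply lost to follow-up".
- **Section 11.3.5** says of patients who cannot attend that "they will be followed up remotely (phone, skype and/or email) so that no data is missed". Adverse and serious adverse events are among the items collected this way.
- **Section 11.9** says that the site "must use every reasonable measure to obtain follow-up clinical data".
- **Section 18** says that lost or withdrawn patients will be followed by healthcare professionals. The investigator decides the nature and frequency of contact. As an example, "the investigator may deem it acceptable to follow up via telephone call, where they may be asked about adverse events".

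Section 10.3 asks for accounting of these patients in the interim and final analyses: "A complete accountability report, along with the explanation for lost-to-follow-up, death, revision, and withdrawn patients".

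**The concern.** Revision is a dated event that a patient can report by telephone, so missing clinic visits need not mean losing the primary endpoint. Section 9.5 nevertheless lets a site end a patient's participation because visits or assessments were missed, and it attaches no duty to keep asking about revision. A revision after that point may go unrecorded, and the hip would then be censored.

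Kaplan-Meier estimation treats censored hips as having the same later risk as those still followed. If patients who stop attending do worse, H1 survival is estimated too high. The comparator is a fixed rate, so the design has no concurrent control arm in which similar losses could offset the error. An analysis plan cannot repair this later, because data that were not collected cannot be analysed.

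**Working it through.** **1. The text, side by side.**

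- Sections 11.3.5 and 11.9 push towards keeping contact. Section 9.5 permits ending it for non-attendance, which is the situation that 11.3.5 and 11.9 exist to manage.
- Section 18 covers patients who are lost or who choose to withdraw. It does not name patients whom the investigator discontinues for non-compliance. Contact is discretionary, and nothing says that what is learned enters the survival analysis.
- Section 10.3 explains losses but recovers no revisions.
- So no section makes revision status obligatory up to 10 years after a discontinuation for non-compliance.

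**2. The plan's own figure.** Inputs from Section 10.1.1: reference and assumed success 0.93, margin 0.05 (boundary 0.88), one-sided alpha 0.05, power 80%, loss 10%.

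n = [1.645 × √(0.88 × 0.12) + 0.842 × √(0.93 × 0.07)]² / 0.05² = 224.6, so 225, and 225 / 0.90 = 250. Both stated figures reproduce. The formula as printed, with the alternative variance only, gives 161; that is a separate matter and has no bearing here.

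**3. Assumed inputs.** The document gives no revision risk for discontinued patients relative to the rest. Call it k and take k = 1, 2 and 3. The lost share is the planned 10% (25 of 250). This covers loss from every cause, so it is an upper bound for this one clause.

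**4. Complete-case extreme** (lost hips contribute nothing from day 0).

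- Retained patients at 93%: true success is 0.9 × 0.93 + 0.1 × 0.86 = 0.923 for k = 2, and 0.9 × 0.93 + 0.1 × 0.79 = 0.916 for k = 3. The overstatement is 0.7 and 1.4 points.
- True overall success at 93%: observed success is 1 − 0.07 / (0.9 + 0.1k), which is 0.9364 and 0.9417. The overstatement is 0.6 and 1.2 points.
- k = 1: no bias.

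**5. Kaplan-Meier with loss spread evenly over 10 years.** Lost patients count until they leave. Let λ and μ be the constant hazards of retained and lost patients. The observed hazard is

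h(t) = [0.9 λ e^(−λt) + 0.1 (1 − t/10) μ e^(−μt)] / [0.9 e^(−λt) + 0.1 (1 − t/10) e^(−μt)],

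and the estimate tends to exp(−∫h) over 10 years.

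| True overall 93% | λ | μ | Kaplan-Meier | Overstatement |
|---|---|---|---|---|
| k = 2 | 0.00658 | 0.01361 | 0.9330 | 0.30 points |
| k = 3 | 0.00601 | 0.01924 | 0.9355 | 0.55 points |

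Fixing retained patients at 93% instead gives 0.9263 against 0.923 and 0.9226 against 0.916, that is 0.33 and 0.66 points. As a rough check, even loss leaves about half the exposure observed, so the bias should be about half the complete-case value: 0.64 / 2 = 0.3 and 1.17 / 2 = 0.6.

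**6. What it could do to the test, at the complete-case extreme.** With true success at 88%, observed success is 1 − 0.12 / 1.1 = 0.891 (k = 2) or 1 − 0.12 / 1.2 = 0.900 (k = 3). The exact binomial test on 225 needs 207 successes. Its type I error is 3.5% at k = 1, 9.4% at k = 2 and 18.9% at k = 3. These are ceilings for the given k, for the reasons in steps 3 and 5.

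**7. Tipping point.** On all 250 hips a pass needs at least 229 successes. With 16 revisions among 225 observed (209 successes, about 93%), 6 unseen revisions among the 25 lost leave 209 + 19 = 228, and the conclusion reverses. That is 6 / 25 = 24%, about 3.4 times 7%.

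**The case against.** The strongest reply is that the sections form a sequence. Section 9.5 begins with retention, Section 11.3.5 supplies remote visits and Section 11.9 demands tracing. On this reading, discontinuation is only the administrative step once all of that has failed. This is a fair reading, but the text does not say it. Non-compliance is listed as a ground separate from loss to follow-up, with no condition that remote contact was tried first.

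Three stronger readings are tempting, and the document does not support them:

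- **That the patients discontinued are those most likely to be revised, so survival is overstated.** Nothing in the protocol says so. Patients doing well may also stop attending, and then the bias is nil or reversed.
- **That a later revision never reaches the primary analysis.** Section 18 permits telephone follow-up, Section 15.1 asks for revised components to be returned, and the words about follow-up outside the study concern patients who withdraw. Ascertainment is not guaranteed, but neither is it ruled out.
- **That the error is one-sided because the registry finds revisions regardless of clinic attendance.** The protocol gives the registry's rates but not how it ascertains revisions, so this cannot be argued from the document.

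It also stands that the 10% is all loss, most of which this clause may not cause, and that Kaplan-Meier uses the time before loss. Both points reduce the size.

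**Conclusion.** The clause permits avoidable and possibly informative censoring of the primary endpoint, and H1 survival could be overstated. Under the even-loss assumptions, with k = 2 to 3 and 10% loss, the bias is about 0.3 to 0.6 points, or 6% to 12% of the margin (0.3 / 5 and 0.6 / 5). At the complete-case extreme it is about 0.6 to 1.4 points, or 12% to 28%. It is zero if loss is unrelated to revision.

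The relative risk, the timing of loss and the share due to this clause are all assumptions. At a true survival near 93%, a bias of this size would not by itself produce a wrong conclusion, since even 91.6% lies well above the 88% boundary. It would matter if H1 performance were near that boundary. The point is worth acting on because the remedy is cheap and the missing data could not be recovered afterwards.

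**What to change.** 1. In Section 9.5, remove non-compliance with visits and assessments as a ground for ending study follow-up, or state that it ends visits only.
2. State that revision status (yes/no, with date) continues to be collected at each scheduled time point by the remote route of Section 11.3.5, for every patient who has not refused it, and that it enters the survival analysis.
3. Reconcile Sections 9.5, 11.3.5, 11.9 and 18, so that patients discontinued for non-compliance are named and collection of revision status is not left to discretion.

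The cost is protocol wording and one short remote contact per time point for each non-attender. A secondary suggestion is a sensitivity or tipping-point analysis for lost hips. A statistical analysis plan that is not shown may already contain one, so its absence here is not part of the finding.
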